Flagging and screening of potential participants will occur in several ways with the assistance of the school nurses, health aides and administrators (all referred to as “school nurses” below), the asthma coordinator, and the study team. To test this intervention as intended in a real-world setting, we anticipate that most of the flagging and screening will be conducted by the school nurse or asthma coordinator. The school nurses or asthma coordinator will systematically identify and screen children with persistent asthma through a previously-tested web application. The school nurse, asthma coordinator, or study team (as needed) will also conduct a more thorough screening survey to assess eligibility criteria for this study prior to enrollment. If children are found to have mild symptoms (and therefore are not eligible for the study), the children may be re-screened by the school nurse or asthma coordinator to re-assess asthma symptoms at a later time during the screening and enrollment period. Screening and enrollment will occur each year in a rolling fashion from late August through November to enroll all children prior to the onset of peak winter season.

Prior to flagging/screening, the RSCD screening forms and medical-alert forms will be used to populate a student registry into the secure web application. The school nurses may also add children into the registry based on the nurse’s knowledge of students’ health status at his/her school (i.e. if the child has frequent visits to the nurse’s office for asthma attacks). The school nurses may only view and edit information in the web application for children at their school.

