The medications and spacers (if needed) will be purchased through the child’s health insurance. Based on our prior research, we anticipate that most of the children will have some form of either private or public health insurance, with most being insured by Medicaid. If a family does not have insurance or insurance coverage status is uncertain, if there is an unexpected expense despite insurance coverage, and when a family informs us they are unable to pay for the co-payment, we will pay for medications or medication supplies (e.g., spacer, nebulizer mask, etc.). In all instances we will also assist the family in getting insurance, help them to proactively plan for refills of medications, as well as link them with services to help them afford co-payments.

Referrals to Additional Resources:

In the SB-TEAM, the telemedicine provider may also provide referrals to an asthma specialist, Regional Community Asthma Network (RCAN), and New York State Smokers' Quitline, as appropriate.

B) Enhanced Usual Care (eUC) Group:

Similar to children in the SB-TEAM group, children in the enhanced usual care group will receive a symptom assessment using national care guidelines, a recommendation for appropriate preventive medications, and asthma education materials. After screening, baseline and randomization, we will use the web-based screening and report system or fax to send a symptom report to the child's PCP with guideline-based recommendations for preventive care. We also will give all providers a summary of the most current national guidelines. We will provide systematic feedback to the family and providers at the same intervals as in the SB-TEAM group's telemedicine visits, by prompting providers to use care guidelines, and caregivers to schedule recommended follow-up visits with the PCP. PCPs of children in the eUC group will assume responsibility for prescribing appropriate medications during the study. In our prior studies, children in the eUC group improved over time, thus creating a conservative bias.

4. Follow-Up Assessments

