We will follow subjects prospectively through the end of the school year, which will vary from between 7-9 months depending on the timing of enrollment for each subject. The preliminary effectiveness of the study will be assessed by telephone interviews with the caregivers, medical record review, and review of school records including, absenteeism, school nurse records (e.g., visits to nurse, medication use at school), and academic performance records. Research assistants, blinded to the subject's group allocation, will conduct telephone calls with caregivers every other month following the initial baseline to collect the follow-up data. At the end of the study year, a home visit will be conducted for the final follow-up assessment at the end of the school year. While the intervention will only last 7-9 months, we may follow subjects for up to 5 years post their enrollment into the study to collect additional outcome measures. These measures may include medical chart review or additional survey assessments with the primary caregiver. If additional surveys are conducted with the caregiver, we will request verbal permission from the caregiver prior to collecting survey data.

Evaluations will be conducted with school health staff members who administered directly observed therapy to children enrolled in the program and/or completed assessments using the web-based system. Paper surveys will be distributed prior to the end of each school year. Respondents will be asked to complete the survey within a 2 week window and return via fax.

Healthcare providers whose patient(s) were enrolled in the program will also be asked to complete a short evaluation asking for feedback on the process. These surveys will be administered on paper and returned via fax and as a web-based survey with an email invitation.

We will also complete semi-structured interviews with participating school health staff and healthcare providers to gather additional information on program acceptability.

5. Measures

The table below summarizes the outcome measures and covariates that will be collected for this study. The table includes how the data will be collected, validated scales/instruments used, and times of administration.

Clinical Outcomes	Measurement Strategy	Time of Administration
Symptom Severity	Caregiver interview, NHLBI guideline-based items Asthma Control Test (ACT)	Baseline, each follow-up, final Baseline, follow-up 2, final

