The primary analysis of this study aims to assess the effectiveness of the SB-TEAM intervention in reducing asthma morbidity (including symptom-free days post-intervention (follow-ups at 4 mo, 6mo and final) as the primary outcome) compared to an enhanced usual care comparison group in school age children with persistent asthma. We will follow subjects prospectively throughout the school year for clinical outcomes (symptoms, asthma control, health care use), functional outcomes (absenteeism, quality of life), and airway inflammation (FeNO). We will use graphical and numerical summaries to describe the outcomes at each assessment point. If distributional assumptions associated with a particular statistical procedure are violated, appropriate transformations will be made or non-parametric alternatives will be used. In accordance with the intention-to-treat principle, all randomized subjects will be analyzed within the group to which they were assigned; minimal crossover is expected. Hypothesis-driven comparisons will be made to control the family-wise type I error rate at 0.05 (two-sided) for the primary hypothesis.

We will determine whether there are important differences at baseline despite randomization between the SB-TEAM and eUC groups in demographics and background characteristics (age, race, ethnicity, insurance, caretaker education), depression, and cotinine. This will include t-tests (or Wilcoxon Rank Sum test) for continuous variables and chi-square (or Fisher's Exact) tests for discrete variables. These comparisons will enable the identification of control variables for use in analyses evaluating treatment effect.

To test for differences between the SB-TEAM and eUC groups on clinical and functional outcomes at the primary time point, bivariate comparisons will be made using t-tests for continuous variables (number of symptom-free days (SFD), symptom nights, rescue medication use, days absent, quality of life, FeNO,

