and ACT scores), and chi-square tests for discrete variables (acute visits, hospitalizations). In addition, the time-course of treatment response during the follow-up period will be evaluated using a linear mixed model with the primary outcome, SFD at post-intervention, as the response, and treatment condition, treatment by time interaction as independent variables. We will model the repeated assessment post-intervention and assess post treatment effects as well as maintenance gain during the period using appropriate linear contrasts. The analysis will be controlled for baseline symptoms, and variables that are found to differentiate between groups at baseline. The treatment effect will be regarded as fixed and the subjects will be modeled as random effect, with an appropriate variance covariance structure specified. Secondary continuous outcomes will be analyzed in a similar manner. Discrete outcomes will be analyzed by fitting Generalized Estimating Equation model. Appropriate link functions and response probability distributions will be specified.

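### The mixed model for symptom-free days lists no main effect of time, so under common codings its treatment-by-time test mixes change shared by both arms with a difference between arms

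*Combined protocol and SAP*

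**What the plan says.** Section 11, Primary Analysis, names SFD at the 4-month, 6-month and final follow-ups as the primary outcome. It plans t-tests at a primary time point. As an addition, it says that "the time-course of treatment response during the follow-up period will be evaluated using a linear mixed model". The response is SFD after the intervention, "and treatment condition, treatment by time interaction as independent variables". On covariates it adds: "The analysis will be controlled for baseline symptoms, and variables that are found to differentiate between groups at baseline". Time is not among them, and no other part of the documents supplies it.

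The model is meant to "assess post treatment effects as well as maintenance gain during the period using appropriate linear contrasts". The contrasts are not written out. The plan does not say whether time is numeric or categorical, or how treatment is coded. Secondary continuous outcomes are to be handled in a similar way.

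Three other places make a change common to both arms plausible:
- Section 3, part B: "In our prior studies, children in the eUC group improved over time, thus creating a conservative bias".
- Section 1: the enrolment window is set "to enroll all children prior to the onset of peak winter season", so follow-up runs from winter to the end of the school year.
- Section 4: interim follow-ups are by telephone, but "At the end of the study year, a home visit will be conducted for the final follow-up assessment".

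**The concern.** A treatment-by-time term measures a difference in change between arms only if the change common to both arms has its own place in the model. Without a time term, the common change may have nowhere to go except the interaction.

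With 0/1 treatment and linear time, the eUC mean is forced flat across the three visits, and the whole SB-TEAM slope is labelled interaction. With treatment and visit both as class variables, the treatment*time term becomes visit within each arm. Its default 4-df test then asks whether either arm changes at all, which is a question about season as much as about treatment.

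At stake are the results this model is there to give: the time course, the visit-specific effects and the maintenance gain. A maintenance contrast taken within SB-TEAM alone would carry the shared change under any coding.

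**Working it through.** **Inputs from section 11, Sample Size:** SD 2.8, within-subject correlation 0.3, at least two assessments, difference 0.8 SFD, 90% power, final sample 336. Section 3 gives equal allocation, hence 168 per arm. Primary Analysis gives two-sided 0.05 and three visits.

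**Assumptions:** compound symmetry, complete data, equally spaced visits (4, 6 and about 8 months), a constant true effect, and a linear shared rise R from 4 months to final. The documents give no R, so a range is used.

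**The plan's own figure.** The variance of the mean of m assessments is 2.8²(1 + (m − 1)0.3)/m. For m = 2 this is 7.84 × 1.3/2 = 5.096. Then n per arm = 2 × 5.096 × (1.960 + 1.282)²/0.8² = 167.3, rounded up to 168, or 336 in total. This matches the plan.

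**0/1 treatment, linear time, no time term.**
- The fitted eUC mean is constant at R/2. SB-TEAM keeps its own line, so the interaction slope per visit step is R/2 although the true interaction is zero.
- Variance of the slope: 7.84 × 0.7/(168 × 2) = 0.01633, SE 0.1278.
- R = 0.5: 0.25/0.1278 = 1.956, rejection 50%. R = 1.0: 0.50/0.1278 = 3.912, rejection 97.5%.
- Estimated effect at 4 months: 0.8 − R/2. At final: 0.8 + R/2. This gives 0.55 and 1.05 for R = 0.5, and 0.30 and 1.30 for R = 1.0, against a true 0.8 at each visit.
- Variance of the final-visit contrast: 2 × 4.181/168 + 0.01633 = 0.0661, SE 0.257, where 4.181 = 7.84 × 1.6/3. With no treatment effect, the contrast R/2 is falsely significant in 16% (R = 0.5) or 49% (R = 1.0) of trials.

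**Treatment and visit as class variables, no time term, default 4-df test.** The noncentrality is 2 × 168 × (R²/2)/(7.84 × 0.7).
- R = 0.5: 336 × 0.125/5.488 = 7.65, rejection 58%.
- R = 1.0: 336 × 0.5/5.488 = 30.6, rejection 99.8%.

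| Rejection of treatment-by-time, no true interaction | R = 0 | R = 0.5 | R = 1.0 |
|---|---|---|---|
| 0/1 treatment, linear time | 5% | 50% | 97.5% |
| Class-coded term, 4 df | 5% | 58% | 99.8% |

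**Wider range** (2,000 simulated trials per scenario, no true treatment effect, R = 0.4, 0.8 and 1.5): linear time 33%, 89% and 100%; 0/1 treatment by visit indicators 25%, 82% and 100%; class-coded term 37%, 96% and 100%. With a time main effect added, rejection was between 4.4% and 5.7% throughout.

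**What does not move.**
- With −1/+1 treatment coding and linear time, the interaction test stays at about 5%.
- In the class-coded model, a between-arm contrast of change stays at about 5%.
- The treatment effect averaged over the three visits is about 0.00 under no effect and about 0.80 under the alternative in every version, with type I error about 5% and power about 95%.

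**The case against.** The strongest reply is that the omission may be shorthand, and that much depends on choices the plan leaves open. With treatment and visit both as class variables, treatment plus treatment*time gives one free mean per arm and visit. That is the same mean model as the proposed fix. Between-arm contrasts at each visit, and between-arm contrasts of change, are then identical, and the plan says inference will use contrasts. This stands. A reader might infer that any shared change is always reported as a treatment-by-time effect, or that the final-visit effect is overstated in general. The documents do not support either.

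It also stands that the mixed model is additional to the t-tests, which need no time term, and that the size of the shared change is not given. The remark that eUC children improved does not say when or by how much, and improvement before 4 months lies outside the modelled period. Enrolment from late August through November spreads each visit over several calendar months. No direction is stated for any effect of the switch from telephone to home interview. If the shared change were a fall, the signs of the visit biases would reverse.

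The reply does not remove the point. A model fitted exactly as listed with 0/1 treatment gives a wrong interaction test, and nothing in the plan rules that fit out.

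**Conclusion.** The point holds in limited form. The listed model has no time main effect. Under 0/1 treatment coding, or the default test of a class-coded treatment*time term, the treatment-by-time test is not a clean test of a difference in change between arms. With 0/1 treatment and linear time, the 4-month and final effects are also biased, by R/2 in opposite directions. The rejection rates above rest on assumed shared rises, compound symmetry and complete data.

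A reader might go on to conclude that the main treatment comparison is compromised. It is not: the visit-averaged effect, the t-tests and the sample of 336 are unaffected in every version checked. Severity is moderate, confined to the time-course, visit-specific and maintenance results and to the secondary continuous outcomes analysed in the same way.

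**What to change.** State the fixed effects as treatment, visit (4 months, 6 months, final; categorical), treatment-by-visit and baseline SFD, together with any other covariates the plan retains. Test treatment-by-visit on 2 df. Write out the visit-specific and maintenance contrasts, each as a difference between arms. Apply the same specification to the secondary continuous outcomes.

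The cost is a sentence or two in the analysis section. The visit main effect takes two parameters (three visits less one), or none if the class-coded model was intended, since that model already has a mean for each arm and visit. If linear time was intended, a categorical interaction takes one more. No new data or participants are needed, and the sample size does not change.

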This proposed project aims to improve guideline-based asthma care using enhanced communication and screening tools, telemedicine and directly observed therapy of preventive medications in city schools. This intervention is designed to overcome key barriers to guideline-based preventive asthma care among minority, poor children in Rochester, NY. Web-based screening will be used to identify children with persistent or poorly controlled asthma and to send reports to the child's primary care doctor. Children in the SB-TEAM group will receive a telemedicine asthma assessment in school and be prescribed a daily preventive asthma medication to be taken through school-based directly observed therapy. Follow-up telemedicine visits will be completed to make dose adjustments and treatment revisions to optimize guideline based treatment. Intervention functions will be overseen by the asthma coordinator, a registered nurse with extensive training in pediatric asthma, as well as [name], MPH, the study's primary investigator. The overall aim of this study is to evaluate the use of the SB-TEAM intervention for improving guideline based care, enhancing adherence to effective preventive medications and at reducing morbidity among young urban children with asthma.

Study Design:

We propose a two-group randomized trial. Children in participating schools will be systematically screened for asthma severity or control using the web-based system, and 400 eligible children will be assigned randomly to either the SB-TEAM intervention (directly observed administration of preventive asthma medications in school and ongoing monitoring and tailoring of the care regimen using telemedicine) or the eUC comparison condition (asthma screening with symptom reports and guideline-based recommendations for preventive medications sent to the PCP, and systematic feedback to the PCP and caregiver to promote appropriate follow-up care). Randomization will be stratified by the use of preventive medication at baseline and a permuted block design will be used to assure an equal balance of children in each group over time. Following randomization, children will be followed prospectively and systematically for the remainder of the school year.

Subjects and Setting:

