symptom diary will be given to the caregiver for tracking of asthma symptoms throughout the school year. All families will also receive handouts for asthma resources, mental health resources in the community and smoking cessation resources. For home interviews in which the child is not present, we will obtain the parent's permission to meet with the child at the school nurse's office to obtain assent (if necessary), and collect the cotinine and eNO measures. For children randomized to the treatment condition (see below), the baseline assessment will include a detailed asthma medication reconciliation and verification of the child's insurance information.

In instances where a caregiver states that their child (age ≥ 7 years) is unable to provide assent to the study (e.g., a child with autism), the assent form will be waived and the research assistant will document the reason for the assent waiver in the subject's study chart.

In instances when the caregiver who provided consent is unavailable for follow-up, if a different caregiver would prefer to respond to the follow-up assessments, the study will be described in detail and verbal consent will be obtained over the telephone from the new caregiver for completion of the follow-up survey. In rare instances where the child's caregiver changes, written consent will be obtained from the new caregiver.

Participants will be given the option to allow for future contact for other research studies at the time of consent. All participants who provided permission will be added to a future contact database dedicated to childhood asthma research (RSRB #31010).

3. Randomization

Following completion of the baseline assessment, each child will be randomly assigned to either the SB-TEAM group or the enhanced usual care (eUC) group. Randomization will be stratified by the use of a preventive asthma medication, per parent report, at baseline. 200 children in both the SB-TEAM group and the usual care group will be randomized. A permuted block design will be used to assure an equal balance of children in each group over time. The randomization scheme will be independently developed by the Biostatistics Center, and the interviewer will call the Study Coordinator who will provide the subject's ID number and treatment assignment.

A) SB-TEAM Group:

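### The SFD mixed model chooses covariates by baseline imbalance with no stated cutoff and leaves out the randomization stratum; the effect is small and the remedy is wording only

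*Combined protocol and SAP*

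**What the plan says.** The combined protocol and SAP deals with this in three places.

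- **Stratification.** Study Design states: "Randomization will be stratified by the use of preventive medication at baseline and a permuted block design will be used". Section 3 (Randomization) adds the source of the information: "Randomization will be stratified by the use of a preventive asthma medication, per parent report, at baseline".
- **Baseline comparisons.** Section 11, Primary Analysis, will look for important differences between arms in "age, race, ethnicity, insurance, caretaker education), depression, and cotinine". That makes seven candidates. The tests are t or Wilcoxon for continuous variables and chi-square or Fisher for discrete ones. Their purpose is explicit: "These comparisons will enable the identification of control variables for use in analyses evaluating treatment effect". No significance level or standardized difference defines an important difference. The two-sided 0.05 in the same section is set for the primary hypothesis, not for these tests.
- **The SFD mixed model.** Its independent variables are "treatment condition, treatment by time interaction as independent variables". The adjustment sentence then follows: "The analysis will be controlled for baseline symptoms, and variables that are found to differentiate between groups at baseline". The rule reaches further outcomes too: "Secondary continuous outcomes will be analyzed in a similar manner".

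Preventive medication use at baseline appears in neither the model terms nor the candidate list, and no other section says the analysis will adjust for it.

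**The concern.** Under correct randomization, a baseline difference between arms is due to chance. A test for such a difference says nothing about whether the variable predicts SFD. A rule based on it can bring in a variable unrelated to outcome and leave out a strong predictor that happens to be balanced. Because no cutoff is stated, the adjusted model is not known until the arms have been compared. With seven candidates, each in or out, there are 2^7 = 128 possible models.

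The stratum is a special case. It was presumably chosen because it was thought to matter for outcome. Blocking within strata balances it, so an imbalance rule will hardly ever admit it, even if it were added to the list. If a balanced stratum predicts outcome and is left out of the model, the model-based standard error is too wide. At stake are some precision and power, and an SFD model that can be reproduced from the plan alone.

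**Working it through.** **Inputs from section 11, Sample Size:** SD 2.8, within-subject correlation 0.3, at least two assessments per child, final sample 336, difference 0.8 SFD per two weeks, 90% power. Alpha is 0.05 two-sided (Primary Analysis).

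**1. The plan's own figure.** The variance of a child's mean over m assessments is 2.8² × (1 + 0.3(m − 1))/m. For m = 2 this is 7.84 × 1.3/2 = 5.096. SE = √(4 × 5.096/336) = 0.2463. Power = Φ(0.8/0.2463 − 1.96) = 90.1%. The stated 90% at 336 is reproduced, so the sample size is not in question.

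**2. Baseline-adjusted SE.** Assume baseline SFD has SD 2.8 and correlates 0.3 with each follow-up. Adjustment removes 0.3² × 7.84 = 0.706.
- Two assessments: variance 4.390, SE 0.2286, power 93.8%.
- Three follow-ups (4 months, 6 months, final): variance 7.84 × 1.6/3 − 0.706 = 3.476, SE 0.2034, power 97.6%.

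**3. Leaving out the stratum.** Let R² be the share of the remaining variance that the stratum explains. The documents give no value, so a range is assumed.
- SE ratio = 1/√(1 − R²)
- Size = 2 × P(Z > 1.96/√(1 − R²))
- Power, stratum omitted = Φ((0.8/SE − 1.96)/√(1 − R²))
- Power, stratum included = Φ(0.8/(SE√(1 − R²)) − 1.96)

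| R² (assumed) | SE too wide by | Size, stratum omitted | Power omitted → included, m = 2 | Gain, m = 2 (points) | Gain, m = 3 (points) |
|---|---|---|---|---|---|
| 0% | 0% | 0.050 | 93.8% → 93.8% | 0 | 0 |
| 2% | 1.0% | 0.048 | 94.0% → 94.2% | 0.2 | 0.1 |
| 5% | 2.6% | 0.044 | 94.3% → 94.9% | 0.6 | 0.2 |
| 10% | 5.4% | 0.039 | 94.8% → 95.8% | 1.0 | 0.4 |

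**4. Could the rule catch the stratum?** Take 400 randomized, 200 per arm, and assume half the children in each stratum. Significance at 0.05 needs a difference in proportions of about 1.96 × √(4 × 0.25/400) = 0.098, or about 20 children in 200. With blocks of four (assumed; the plan gives no block size), an unfinished block can shift a stratum by at most 2 children, a difference of about 2/200 = 0.01.

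**5. Entry by chance.** For seven independent candidates the chance that at least one is flagged is 1 − (1 − a)^7: 7% at a = 0.01, 30% at 0.05 and 52% at 0.10. Correlated candidates lower this. At the 0.05 cutoff it is 27% with an assumed common correlation of 0.3, and 23% with 0.5.

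**6. Simulation of the rule.** Analysis of covariance on child means, N = 336, two assessments, no attrition, blocks of four, seven independent normal candidates, 100,000 trials per scenario.
- Null size with the rule at 0.05 was 0.050, 0.048, 0.044 and 0.039 for stratum R² of 0%, 2%, 5% and 10%. With baseline symptoms plus the stratum it was 0.049 to 0.051.
- Cutoffs of 0.01 to 0.20, applied mechanically, gave sizes of 0.037 to 0.050 across the null scenarios, including candidates that each explain 2%.
- The mean estimate stayed within 0.0011 SFD of the truth.
- When a covariate entered, the estimate moved from the baseline-symptoms-only result with SD 0.032 SFD (non-prognostic candidates) or 0.088 SFD (2% each), against a target of 0.8.
- Under the null, the verdict differed between cutoffs of 0.01 and 0.10 in 0.6% to 1.6% of trials.

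**The case against.** The strongest reply is that nothing serious goes wrong. The rule uses baseline data only. The candidates and tests are named, and baseline symptoms, the covariate most likely to matter, are fixed. All of that stands. What remains open is the cutoff, the final covariate set and the stratum.

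The plan also has unadjusted comparisons, introduced with "To test for differences between the SB-TEAM and eUC groups on clinical and functional outcomes at the primary time point", and does not say whether those or the mixed model decide the trial. If the t-test decides, this point concerns a supporting analysis. That limits its weight, but the mixed-model text is still incomplete.

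The sizes rest on assumptions. The documents give no prognostic strength for the stratum or any candidate, so zero is as compatible with them as 10%. The primary outcome covers three follow-ups, so the smaller power gains are the more relevant ones. The near-impossibility of flagging the stratum depends on the block size and on which children are compared, so it is right to say very unlikely and no more.

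A reader might infer two stronger things that the documents do not support.

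- **That type I error is inflated.** This would need someone to run several cutoffs and report the most favourable. Taking the smallest p of five versions gave a simulated size of 0.055 to 0.062. A missing cutoff leaves the possibility open, but the plan does not propose it.
- **That naming covariates in advance gains about two power points.** The simulated contrast of 94.1% under the rule and 96.1% with covariates fixed requires all seven candidates in the model, each independently explaining an assumed 2%. That is not the gain from adding the stratum.

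**Conclusion.** The point holds as a minor one. The SFD mixed model is not fully specified in advance, its selection rule follows chance imbalance, and it omits the one factor the trial stratifies on. The treatment estimate is not biased and 336 evaluable (400 enrolled) is unaffected. Applied mechanically, the test is nominal or somewhat conservative. Within the assumed 0% to 10% range for the stratum, the loss is at most about one power point with two assessments and under half a point with three. The textual gaps do not depend on any of these assumptions; only the sizes do.

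**What to change.** - In Primary Analysis, list the covariates of the SFD mixed model in advance: baseline symptoms, preventive medication use at baseline (the randomization stratum), and any prognostic variables named before outcomes are analysed by arm.
- Use the same approach in the mixed models for secondary continuous outcomes.
- Keep the baseline comparisons as description and stop using them to choose covariates. Adjustment for variables found imbalanced can stay as a labelled sensitivity analysis.

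The cost is a change of wording. The stratum takes one degree of freedom and is already recorded for every child, because randomization uses it. Any further named covariate costs its own degrees of freedom. No new data and no change in sample size are needed.
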